	
All device systems are on the market in Japan, and will be implanted per standard of care (SOC) and BSC Instructions for Use (IFU) for the respective devices should be followed.
 
Neither the devices nor the implant procedure are part of this study. The decision as to which device any subject receives is to be determined by the investigator and is not part of this study.
 
Device system use and programming will need to follow SOC, devices IFUs and must follow CIP programming requirements. All devices in the study must be intended to be connected to the Latitude system.

Study Design	
This is a prospective, non-randomized, multicenter, multi-cohort clinical outcome registry study to evaluate SOC.

Planned Number of Subjects	
It is planned to enroll a minimum of 556 to power all primary endpoint for each cohort.
 
As soon as a minimum of 556 eligible subjects are entered into the study database, the closure of enrolment can begin. The maximum number of followed study subjects is 950.
 
The event dependent character of the study, and the calculated necessary minimum sample size may allow early enrollment closure of the study enrollment.

Planned Number of Investigational Sites / Countries	
Approximately 40 investigational sites in Japan will be included. If a site does not enroll a subject within a 3-month time period, the site may be closed for enrolment and replaced at the discretion of the sponsor.

Primary Safety Endpoint(s)	
Not applicable

Heart Failure Indication and Sudden Cardiac Death Prevention Trial Japan
HINODE

Primary Effectiveness Endpoints	
Defibrillator Cohort (including ICD and CRT-D Cohorts): Composite rate of first appropriately treated ventricular arrhythmia (by anti-tachycardia pacing [ATP] or shock) or life-threatening symptoms associated to ventricular arrhythmia (defined as hemodynamic instability which requires treatment), whichever comes first under MADIT Arm B or C programming conditions in a study population with a majority of Japanese subjects
 
PM/CRT-P Cohort: All-cause mortality in subjects with a maximum of 3 risk factors (analyzed for MADIT II data)
 
Non-device Cohort (ESC Guideline 2016 Indicated but not implanted): All-cause mortality in the subject cohort with 2 to 5 predefined SCD driving risk factors

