Statistical Test Method	
Sample Size Methodology:
 
 Sample size for each primary endpoint was calculated using exact binomial methods for comparison of a single proportion to a performance goal. 
Analysis Methods:
 
 For ICD treated subjects, the ventricular arrhythmia associated symptoms free-rate from implant will be calculated as the proportion of actively enrolled subjects without an appropriately treated ventricular arrhythmia associated symptom through 12 months after implant. The null hypothesis will be rejected and the endpoint considered met if the lower one-sided 97.5% confidence bound for the proportion of subjects with no appropriately treated ventricular arrhythmia associated symptoms is greater than 85.0%. For CRT-D treated subjects, the ventricular arrhythmia associated symptoms free-rate from implant will be calculated as the proportion of actively enrolled subjects without an appropriately treated ventricular arrhythmia associated symptom through 12 months after implant. The null hypothesis will be rejected and the endpoint considered met if the lower one-sided 97.5% confidence bound for the proportion of subjects with no appropriately treated ventricular arrhythmia associated symptoms is greater than 87.0%.

Heart Failure Indication and Sudden Cardiac Death Prevention Trial Japan
HINODE

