Statistical Test Method (continued)	
 • The primary endpoints above will be performed for ICD and CRT-D cohorts combined (primary analysis) as well as for ICD and CRT-D treated subjects separately (for descriptive purpose). • For PM/CRT-P treated subjects, the all-cause mortality free-rate (survival rate) from implant will be calculated as the proportion of actively enrolled subjects who are alive 12 months after implant. The null hypothesis will be rejected and the endpoint considered met if the lower one-sided 97.5% confidence bound for the proportion of subjects with no death is greater than 80.0%. • For Non-device subjects (ESC Guideline 2016 Indicated but not implanted), the all-cause mortality free-rate (survival rate) from enrolment will be calculated as the proportion of actively enrolled subjects who are alive 12 months after enrolment. The null hypothesis will be rejected and the endpoint considered met if the lower one-sided 97.5% confidence bound for the proportion of subjects with no death is greater than 80.0%. • Exploratory analyses for ICD and CRT-D Cohorts combined versus Non-Device Cohort (ESC Guideline 2016 Indicated but not implanted): propensity score matching comparison of all-cause mortality rate and composite rate of HF events between pooled cohorts with device (ICD and CRT-D) versus the Non-Device Cohort regarding 7 risk factors at baseline (NYHA Class III or IV, renal dysfunction [chronically BUN >26 mg/dL / ≥ 9.28 mmol/L], diabetes type I and II, chronic atrial fibrillation [permanent or persisting according to ESC Guideline 2016], prior MI, age >70 years, smoking today or during last 5 years). 
Further details on analytical methods can be found in Section 12 of the CIP

Sample Size Parameters	
ICD Treated Subjects:
 
The minimum required sample size to statistically power the ventricular arrhythmia associated symptoms free-rate through 12 months post implant is 117 subjects. Sample size was calculated assuming a 95.0% ventricular arrhythmia associated symptoms free-rate, a performance goal of 85.0%, one-sided alpha level of 0.025, 90% power, and 20% attrition.

Heart Failure Indication and Sudden Cardiac Death Prevention Trial Japan
Hinode

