12.1.1.1. Hypotheses

The null and alternative hypotheses are as follows:

H_0 : The ventricular arrhythmia associated symptoms free-rate from 0-12 months $\leq 85.0\%$

H_A : The ventricular arrhythmia associated symptoms free-rate from 0-12 months $> 85.0\%$

The null hypothesis (H_0) will be rejected if the lower one-sided 97.5% confidence bound for the ventricular arrhythmia associated symptoms free-rate is greater than the performance goal of 85.0%.

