12.1.1.2. Statistical Methods

When the final study subject reaches the final CIP required follow-up visit, the primary analysis will be performed based on the Kaplan-Meier method for the estimation of the 12-month ventricular arrhythmia associated symptoms free-rate, including the lower 97.5% confidence bound (computed based on log-log methodology). This Kaplan-Meier analysis will begin at the time of implant. Subjects that withdraw consent or are lost-to-follow-up prior to the 12-month endpoint evaluation will be censored at their date of last contact. All subjects actively enrolled will be included in the endpoint analysis.

The null hypothesis will be rejected and the endpoint considered met if the lower 97.5% confidence bound for the ventricular arrhythmia associated symptoms free-rate at 12 months is greater than 85.0%.

Additionally, a Kaplan-Meier survival time-to-event curve along follow-up will be provided.

The primary analysis above will be performed for CRT-D and ICD cohorts combined as well as for ICD treated subjects separately.

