12.1.2.1. Hypotheses

The null and alternative hypotheses are as follows:

H_0 : The ventricular arrhythmia associated symptoms free-rate from 0-12 months $\leq 87.0\%$

H_A : The ventricular arrhythmia associated symptoms free-rate from 0-12 months $> 87.0\%$

The null hypothesis (H_0) will be rejected if the lower one-sided 97.5% confidence bound for the ventricular arrhythmia associated symptoms free-rate is greater than the performance goal of 87.0%.

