12.1.2.2. Statistical Methods

When the final study subject reaches the final CIP required follow-up visit, the primary analysis will be performed based on the Kaplan-Meier method for the estimation of the 12-month ventricular arrhythmia associated symptoms free-rate, including the lower 97.5% confidence bound (computed based on log-log methodology). This Kaplan-Meier analysis will begin at the time of implant. Subjects that withdraw consent or are lost-to-follow-up prior to the 12-month endpoint evaluation will be censored at their date of last contact. All subjects actively enrolled will be included in the endpoint analysis.

The null hypothesis will be rejected and the endpoint considered met if the lower 97.5% confidence bound for the ventricular arrhythmia associated symptoms free-rate at 12-months is greater than 87.0%.

Additionally, a Kaplan-Meier survival time-to-event curve along follow-up will be provided.

The primary analysis above will be performed for CRT-D and ICD cohorts combined as well as for CRT-D treated subjects separately.

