12.1.5. Secondary Endpoints

- The secondary endpoint for subjects implanted with CRT-D/ICD is:
 - All-cause mortality rate
- The secondary HF endpoints for subjects with device implanted include:
 - Composite rate of HF events in ICD, CRT-D, and PM/CRT-P cohorts, which require IV treatment, HF related hospitalization, or led to HF death
 - Therapeutic sustainability at 1 year in ICD, CRT-D, and PM/CRT-P cohorts, defined as free of qualified SADEs post successful implantation, such as re-implant procedure, required invasive procedure related to the device system, pacing exit block, all-cause infection, and death due to therapy failure in comparison with data from MADIT CRT, MADIT RIT, Optimind, and Rally X4 studies.
- The secondary endpoint for subjects implanted with CRT-D/ICD and non-device subjects is:
 - Comparison of rate of sudden cardiac death in the non-device cohort with the rate of appropriately treated ventricular arrhythmias or sudden cardiac death in the defibrillator cohort (ICD cohort and CRT-D cohort)

Secondary analyses will be descriptive and exploratory. Detailed statistical methods for these endpoints will be presented in a Statistical Analysis Plan (SAP).

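### The pooled ICD and CRT-D analysis is called primary, but only the separate cohorts have hypotheses, goals and sample sizes, so the primary defibrillator test has no single success threshold

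*Combined protocol and SAP*

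**What the plan says.** **Pool as primary.** The Synopsis (Primary Effectiveness Endpoints) lists one endpoint for one group: "Defibrillator Cohort (including ICD and CRT-D Cohorts): Composite rate of first appropriately treated ventricular arrhythmia". Section 7.1 does the same. Under Statistical Test Method, the Synopsis says the analysis is "performed for ICD and CRT-D cohorts combined (primary analysis) as well as for ICD and CRT-D treated subjects separately (for descriptive purpose".

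**Cohorts as the units tested.** The same Synopsis block gives ICD and CRT-D a rule each, both opening "The null hypothesis will be rejected and the endpoint considered met if the lower one-sided 97.5% confidence bound for the proportion of subjects with"; one ends at 85.0% and the other at 87.0%. Section 12.1.1.1 rejects the ICD null hypothesis if the lower bound for the "free-rate is greater than the performance goal of 85.0" percent. Section 12.1.2.1 does so for CRT-D if the bound for the "free-rate is greater than the performance goal of 87.0" percent. Table 12.1-1 has an ICD row (expected 95%, 93 for analysis, 117 enrolled) and a CRT-D row (expected 97%, 76 and 95). It has no pooled row.

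**One pool under both rules.** Directly after the 85% rule, section 12.1.1.2 says: "The primary analysis above will be performed for CRT-D and ICD cohorts combined as well as for ICD treated subjects separately". Directly after the 87% rule, section 12.1.2.2 says: "The primary analysis above will be performed for CRT-D and ICD cohorts combined as well as for CRT-D treated subjects separately". Neither section calls the separate analyses descriptive.

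**Deferral.** Section 12.1.5 says: "Secondary analyses will be descriptive and exploratory. Detailed statistical methods for these endpoints will be presented in a Statistical Analysis Plan (SAP". That covers secondary endpoints. Sections 12.3 and 12.3.1 defer propensity matching and the ancillary assessments in the same way. Nothing defers the primary success rule.

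**The concern.** A primary endpoint needs one hypothesis and one rule for calling it met. Here the text supports three: the pool against 85%, the pool against 87%, or each cohort against its own goal. They can give different answers from the same data, and nothing says which one governs.

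The analysis labelled primary has no null hypothesis, goal, expected rate or sample size of its own. The analyses that have all of these are demoted to descriptive in the Synopsis, although both the Synopsis and section 12.2.2 justify the minimum of 556 subjects as powering the primary endpoint of each cohort.

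Section 12.3.7 requires changes to the planned analyses to be documented. Choosing between two goals that already stand in the protocol might not be regarded as a change, so the choice could be made late without a record.

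**Working it through.** **1. The plan's own figures.** Exact binomial test, one-sided alpha 0.025. Take the smallest r with P(X ≥ r | goal) ≤ 0.025, then the smallest n with P(X ≥ r | expected rate) ≥ 0.90.

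- ICD, goal 85%, expected 95%: n = 93, success at 86 or more event-free, alpha 0.0235, power 0.906. Enrolled: 93/0.80 = 116.25, so 117.
- CRT-D, goal 87%, expected 97%: n = 76, success at 72 or more, alpha 0.0241, power 0.922. Enrolled: 76/0.80 = 95.
- 117 + 95 + 172 + 172 = 556.

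All match Table 12.1-1. The cohort sizes are correct.

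**2. Pool size.** All actively enrolled subjects are analysed (12.2.1), so the minimum pool is 117 + 95 = 212 and the maximum is 270 + 250 = 520. If only the numbers needed for analysis are evaluable, it is 93 + 76 = 169.

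**3. Pooled cut-offs.** Without censoring, the Kaplan-Meier estimate is p = x/n and the log-log lower bound is L = p^exp(1.96 × SE), with SE = √((1 − p)/(np)) / |ln p|. Smallest event-free count with L above the goal:

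| Pool n | Goal 85% | Goal 87% | Events that meet 85% but miss 87% |
|---|---|---|---|
| 169 | 153 | 156 | 14–16 |
| 212 | 191 | 195 | 18–21 |
| 520 | 459 | 468 | 53–61 |

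Exact binomial bounds give the same cut-offs.

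**4. Chance that the two goals disagree for the pool.** At the planned rates the event-free count is Bin(117, 0.95) + Bin(95, 0.97), a pooled rate of (117 × 0.95 + 95 × 0.97)/212 = 95.9%. The other columns use one common rate.

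| Pool n | Planned | 95% | 93% | 91% | 90% |
|---|---|---|---|---|---|
| 212, no censoring | 0.3% | 2.0% | 18.9% | 36.4% | – |
| 212, 20% attrition | 0.6% | 3.0% | 19.8% | 31.6% | – |
| 520, no censoring | about 0% | about 0% | 0.4% | 17.5% | 37.8% |

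The attrition row is a Kaplan-Meier simulation (Greenwood variance, log-log bound). Its assumptions are not in the documents: exponential event times, 20% of subjects censored uniformly over 12 months, and independent cohorts.

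**5. Pool against cohorts.** At 117 and 95, the cohort rules require at least 108 and 90 event-free (at most 9 and 5 events). At the planned rates without censoring, the cohorts pass with probability 0.931 and 0.933, and both pass with 0.931 × 0.933 = 0.869. The pool clears 87% (hence also 85%) while at least one cohort misses its own goal with probability 0.128. With 20% attrition the simulation gives 0.809 for both cohorts passing and 0.185 for the conflict. At 270/250, without censoring, the conflict is about 0%.

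Example: 5 events in 117 ICD subjects and 6 in 95 CRT-D subjects.

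- Pool, 201/212: p = 0.9481, SE = 0.3015, L = 0.9481^exp(0.591) = 90.8%. Clears both goals.
- ICD, 112/117: L = 90.0%. Clears 85%.
- CRT-D, 89/95: L = 86.5%. Misses 87%.

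**6. Power and error rate.** At n = 212 and the planned rates, the pool passes with probability above 99.9% against 85% and 99.7% against 87%. When the true pooled rate equals the goal, the pass rate is 2.0% (85%) and 1.6% (87%), so a single pooled test stays within 2.5%.

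**The case against.** The best counter-argument concerns weight. At the planned rates the two pooled goals disagree in only 0.3% of studies at 212 subjects and almost never at 520. The 19% to 38% figures need pooled event rates of 7% to 10%, against about 4.1% planned. The 12.8% is close to one minus the joint power of the two cohort tests (1 − 0.869 = 13.1%), and the plan never says both must pass. These points stand as a description of size. But the study asks whether US and European data carry over to Japan, so rates away from plan are possible. The 12.8% also remains a conflict in the text, because the Synopsis and section 12.1.2.2 give CRT-D its own rule for calling the endpoint met.

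A second argument is that section 12 is the detailed text, so the cohort tests govern and the Synopsis labels are stray. That reading is workable but not conclusive: section 7.1 and the Synopsis name one Defibrillator Cohort, and section 12 itself tests the pool twice.

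Third, a separate SAP might fix a pooled goal. It was not available to check. The protocol does not defer this rule to it, and the contradiction inside the protocol would remain.

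Fourth, it could be argued that sponsor staff who see events (17.4, 22.1) might pick the goal with results in view. That is speculative: no interim analysis is planned (12.3.2) and an event committee classifies primary events (22.2). The conclusion does not rest on it.

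**Conclusion.** The point holds. The analysis named primary has no threshold of its own, section 12 places the pool under two, and no other text resolves this. The stated decision rules conflict; this is more than missing detail.

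Under the plan's assumptions the conflict between 85% and 87% rarely matters. It becomes material if the true pooled rate is about 93% or lower at the minimum enrolment, or about 91% or lower at the maximum. The conflict between pool and cohorts is 12.8% at the minimum enrolment under the planned rates, or 18.5% with the assumed attrition pattern, and vanishes at the maximum. The plan permits closing enrolment at the minimum. Power is not in question, and no inflation of type I error is claimed. The need to fix this rests on the undefined success rule for a primary endpoint.

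**What to change.** Choose one route before database lock and before results are seen.

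**Route 1: pool primary** (follows section 7.1 and the Synopsis labels). State one pooled null and alternative hypothesis with one goal fixed now as a number. Footnote 1 of Table 12.1-1 sets each goal 10 points below the expected rate. Applied to the pool, this gives (117 × 85% + 95 × 87%)/212 = 85.9%. Over the permitted mixes it runs from (270 × 85% + 95 × 87%)/365 = 85.5% to (117 × 85% + 250 × 87%)/367 = 86.4%, so the number must be fixed and not left to the final mix. At 85.9%, power under the planned rates is 99.6% at n = 169 and 99.9% at n = 212. Add a pooled row to Table 12.1-1 and mark the cohort analyses as descriptive, without a test.

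**Route 2: cohorts confirmatory, pool descriptive.** State whether both must succeed. If both must, joint power is 0.906 × 0.922 = 83% at 93/76 evaluable (independent cohorts), or about 81% at 117/95 enrolled under the simulated attrition. If either suffices, add a multiplicity rule, because two independent 2.5% tests allow up to 1 − 0.975² = 4.9%.

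Under either route, align the Synopsis (planned number of subjects, primary endpoints, hypotheses, test methods, sample size) and sections 7.1, 12.1.1 to 12.1.2.2, 12.1.6 with Table 12.1-1, 12.2.2 and 12.3.4.

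The cost is wording, plus one table row under Route 1. Neither route needs new subjects or data. Route 2 with both required accepts lower joint power at the minimum enrolment.

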The present study is intended to evaluate the risk of SCD and heart failure (HF) events in known high risk subject cohorts. Implantation of pacing and defibrillation devices that provide cardiac resynchronization therapy (CRT) is proven to be a highly effective treatment for selected subjects with cardiac arrhythmia and HF. However, the question remains whether study data from the United States (US) and Europe are fully applicable in Japan despite genetic and cultural differences. Implantable cardioverter-defibrillator (ICD) and cardiac resynchronization therapy-defibrillator (CRT-D) devices for many patients with high risk on SCD have not been studied in a prospective study in Japan. Therefore, this registry study intends to collect clinical data in defined ICD and CRT-D treatment cohorts in a study population with a majority of Japanese subjects so that further knowledge is added to improve medical device treatment options.

An optimized ICD treatment was studied in the Automatic Defibrillator Implantation Trial (MADIT) Reduce Inappropriate Therapy (RIT) trial^{3,4} where 1500 subjects from US and Europe have been enrolled in 3 arms. Arm B and Arm C, with a high cut off rate of >200 bpm and with a prolonged delay in therapy at 170 bpm have shown a significant reduction in unnecessary and inappropriate treatment.⁴

The mortality rate in pacemaker cohorts is usually very high and it is the question whether a different device therapy may help selected patient cohorts. The defined cohort in this HINODE study is selecting especially subjects with a heart failure background which have a high incidence of further progression of the disease.⁶ It is the question whether those subjects can be identified during de novo implants or during device replacement so that a different device therapy would have the potential to impact the progression of the disease. The selected cohort has at least 3 risk factors which may lead to an increased incidence of Non-sustained ventricular tachycardia (NSVT) or other ventricular arrhythmia. The use of a risk score in a PM population may help to identify subjects who may benefit from CRT-P or CRT-D.

The outlined risk factor MI in the HINODE study is used for subjects with one or more clinically documented, enzyme-positive myocardial infarctions, or clear evidence of pathologic Q waves or generally accepted imaging techniques.

The rate of appropriate first treatments (anti-tachycardia pacing [ATP] or shock) will be considered as treatment of potential life-threatening arrhythmias. The present study will use the MADIT RIT ICD programming for ICD and CRT-D devices and will compare the rate of appropriate treatments in MADIT RIT⁴ with the rate observed under the same programming conditions in the present study. The study results will be compared with data from

multicenter automatic defibrillator implantation trials (MADITs) conducted in US and Europe.

In addition to the evaluation of first appropriate treatment, life-threatening ventricular arrhythmias, clinical HF events will be evaluated.

Special attention will be given to known risk markers at enrolment throughout the study so that a risk score may be developed to provide guidance in optimized therapy decisions.

The sample size will provide sufficient data to allow the identification of high risk subgroups, especially in the ICD and pacemaker (PM) cohorts. These data will also allow an assessment of European and US study data being transferable to the Japanese specific environment due to similar clinical observations.

The selected cohort of PM subjects has an expected and unstudied elevated risk of developing increased HF symptoms or may be at risk of SCD. The required home monitoring system will allow early detection of ventricular arrhythmias and may serve as early indicator for left ventricular ejection fraction (LVEF) and QRS evaluation. The same LVEF and QRS evaluations will be associated with HF admissions ('HF admission' comprises the following conditions: admission to hospital because of HF and/or intravenous (IV) therapy of HF and/or upgrade of the PM/CRT-P) so that an unknown need for changed device therapy can be identified. CRT is recommended for subjects with HF with reduced ejection fraction (HF_rEF; LVEF: <40%) and QRS >130 ms; ICD therapy is recommended for subjects with LVEF ≤35% especially if this is associated with additional risk factors e.g. prior MI, diabetes type I and II, etc.

In large European registries and European diabetes guidelines, it has been described that diabetic post myocardial infarction (MI) patients with a mid-range LVEF of 40-49% (HF_mEF) have an elevated risk of SCD. Since there are no event data available for Japanese patients, this registry will also include a group of subjects who have combined risk factors of post MI, diabetes type I and II, and an LVEF ≤35% but have not received device treatment to collect baseline data on event rates and disease progression in a study population with a majority of Japanese subjects.

5. Device Description

Implanted subjects will receive one of 4 types of Boston Scientific (BSC) devices prior to enrolment in the study:

1. ICD (only MRI conditionally safe systems) + Latitude
2. CRT-D (IS4 connector only, MRI conditionally safe systems) + Latitude
3. PM + Latitude
or
4. CRT-pacemaker (CRT-P) + Latitude

All device systems are on the market in Japan, and will be implanted per standard of care (SOC) and BSC Instructions for Use (IFU) for the respective devices should be followed.

Neither the devices nor the implant procedure are part of this study. The decision as to which device any subject receives is to be determined by the investigator and is not part of this study.

Device system use will need to follow SOC, devices IFUs and must follow CIP programming requirements.

The programming of the devices is to be documented in the subject's electronic Case Report Form (eCRF) as part of the enrolment criteria (Section 9). As part of the programming, all subjects must be intended to be connected to the Latitude system.

If patients cannot be connected to Latitude more than 6 months after enrolment, a deviation needs to be completed and a reason needs to be given. In addition, endpoint related data can be uploaded into the database by the site (e.g. electrogram (EGM) for ventricular arrhythmias).

A device deficiency reporting might need to be completed.

[figure not shown]
6. Study Objectives

The purpose of this cohort therapy study is to collect clinical event and outcome data in a study population with a majority of Japanese subjects on SCD, HF events, and appropriately treated ventricular adverse events in predefined subject cohorts. These event rates will be compared with available data mainly from Europe and the United States. It is the intention to add evidence in Defibrillator treatment and treatment with CRT-D devices.

Selected Subject Cohorts:

1. Selected subject cohort with criteria for SCD (without spontaneous prior ventricular sustained arrhythmia) and de novo implanted Defibrillator device treatment (ICD).
2. Selected subject cohort with criteria for SCD and widely accepted standard CRT indication who received a de novo implanted CRT-D device treatment.
3. Selected subject cohort who are clinically expected to require >40% right ventricular pacing with an LVEF $\leq 50\%$, any determined New York Heart Association (NYHA) Class, and receiving PM or CRT-P therapy despite previous device history (de novo, box changes, system revisions or upgrades).
4. Selected subject cohort with criteria for SCD fulfilling European Society of Cardiology (ESC) ICD or CRT-D therapy guidelines (2016) with an LVEF $\leq 35\%$, having 2 to 5 predefined risk factors but do not have or have had a cardiac implanted device ICD, CRT-D, PM, or CRT-P.

Figure 3.2-1: HINODE Sample Size

7. Study Endpoints

